### 3.1.10 Subject Withdrawal from Treatment or from Study

A subject will be **withdrawn from study treatment** for any of the following reasons:

1. Pregnancy or intent to become pregnant.
2. Clinical, symptomatic or radiographic progression warranting alternative treatment.
3. Significant protocol violation or noncompliance that, in the opinion of the Investigator or Sponsor, warrants withdrawal.
4. Initiation of alternative anticancer therapy including another investigational agent.
5. Development of intercurrent, non-cancer related illnesses that prevent either continuation of therapy or regular follow-up.
6. Withdrawal of consent for further treatment.

7. Best medical interest of the subject (at the discretion of the Investigator)
8. Discontinuation criteria per Section 8.3.

Subjects who are withdrawn from study treatment should undergo the planned On Study Follow-up through 100 days after the last study drug administration (see the Study Flowchart in Section 3.2) and enter the Post Study Follow-up phase (see Section 3.1.16).

A subject will be **withdrawn from the study** for the following reasons:

1. Best medical interest of the subject (at the discretion of the Investigator)
2. Withdrawal of consent for all follow-up.
3. Lost to follow-up
4. Death

### **3.1.11 Subject Evaluability and Subject Replacement**

Subjects in Cohort A are fully evaluable for safety review of the concurrent ipilimumab and nivolumab therapy if:

- 1) they receive at least 1 dose of ipilimumab, nivolumab, or RT and have a Grade 3 or 4 related AE
- 2) In the absence of a Grade 3 or 4 related AE, they fulfill the criteria for the Per-protocol population for safety and tolerability as defined in Section 4.1.2.

Subjects in Cohort A who are not fully evaluable for safety review will be replaced.

Subjects are considered evaluable for the secondary efficacy endpoints if they fulfill the Per-protocol and Intent to treat populations described in Section 4.2.2, or if they discontinue from the study due to symptomatic progression, death, or toxicity at any point.

Subjects who discontinue the study and do not meet evaluability criteria may be replaced.

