**Objectives and Synopsis**

This is an open-label, multicenter pilot Phase 1 study of the checkpoint antibodies ipilimumab and nivolumab in combination with radiotherapy (RT) in 18 subjects with unresectable stage IV melanoma. All subjects will receive concurrent ipilimumab (3 mg/kg) and nivolumab (1 mg/kg) every 3 weeks for 4 doses, followed by nivolumab monotherapy (240 mg every 2 weeks). Note: per Amendment 5, nivolumab monotherapy continuing after Week 18 may be given as 480 mg every 4 weeks. Radiotherapy will be initiated after the first dose and before the second dose of immunotherapy.

There will be 2 cohorts in the study. Subjects in Cohort A will initially receive a conventional total palliative dose of 30 Gy delivered over 2 weeks in 10 fractions of 3 Gy each. Once 9 subjects have been accrued to Cohort A and completed the concurrent ipilimumab and nivolumab therapy, if  $\leq 7$  subjects have Grade 3 or 4 drug- or radiation-related adverse events, the safety of Cohort A will be deemed acceptable and additional subjects will be accrued to Cohort B (see exception in Section 3.1, i.e., asymptomatic amylase and lipase abnormalities are not included). Subjects in Cohort B will receive the high-dose hypofractionated RT for which treatment of a target lesion will comprise a total palliative dose of 27 Gy delivered over 2 weeks in 3 fractions of 9 Gy each.

The primary objective is the assessment of safety according to the National Cancer Institute (NCI) Common Terminology Criteria for Adverse Events (CTCAE), Version 4.03.

The secondary objectives are to evaluate: (1) objective response rate (ORR) at Weeks 12 and 18, (2) disease control rate (DCR) at Weeks 12 and 18, (3) duration of response, (4) progression-free survival (PFS), and (5) overall survival (OS).

The exploratory objectives are to perform correlative studies investigating the immunological effects of ipilimumab and nivolumab with RT.

Assessment methods include the NCI CTCAE (Version 4.03) for safety and the modified Response Evaluation Criteria for Solid Tumors (RECIST) 1.1 (primary) and immune-related RECIST (irRECIST; secondary) for clinical efficacy.

Sponsor: Ludwig Institute for Cancer Research, New York, NY	Study Chair: [REDACTED]
Sponsor representative Signature & Date	Study Chair Signature & Date

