#### Cohort A:

Subjects in Cohort A will initially receive a conventional total RT palliative dose of 30 Gy delivered over 2 weeks in 10 fractions of 3 Gy each. Once 9 subjects have been accrued to Cohort A and completed the concurrent ipilimumab and nivolumab therapy, if  $\leq 7$  subjects have Grade 3 or 4 drug- or radiation-related AEs, as per Section 3.1.6, the safety of Cohort A will be deemed acceptable and additional subjects will be accrued to Cohort B.

Note: Grade 3 or 4 amylase or lipase abnormalities that are not associated with clinical symptoms will not be included in the Cohort A safety assessment described above.

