### 3.1.6 Sample Size and Statistical Considerations

This study is intended to generate descriptive safety data. Nine subjects are anticipated for each cohort to enable a variety of disease presentations and RT targets.

Prior experience with nivolumab and ipilimumab administered in combination has been associated with a treatment-related grade 3/4 toxicity rate of 53%. A rating of Grade 3/4 drug- or radiation-related toxicity is considered to be acceptable in Cohort A if  $\leq 7$  of 9 subjects (78%) are affected (see exception in Section 3.1, i.e., asymptomatic amylase and lipase abnormalities are not included). This number was selected to avoid premature closure of exploration of this approach.

As this is the first prospective study of RT plus ipilimumab and nivolumab, no historical controls are available to anticipate the rate of toxicity of this triple combination regimen.

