### 3.1.9 Dose-limiting Toxicity

The DLT and MTD will not be defined or determined. A safety review will be conducted when 9 subjects have been accrued to Cohort A and completed the concurrent ipilimumab and nivolumab therapy. If  $\leq 7$  subjects have Grade 3 or 4 drug- or radiation-related AEs, the safety of Cohort A will be deemed acceptable and additional subjects will be accrued to Cohort B. The Cohort A assessment period for this evaluation will include the first 2 cycles of treatment, up to and including the pre-dose safety assessments scheduled for Cycle 3 (see Section 4.1.2).

Note: Grade 3 or 4 amylase or lipase abnormalities that are not associated with clinical symptoms will not be included in the Cohort A safety assessment described above.

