#### 4.1.2 Subject Evaluation & Statistics

The Intent-To-Treat (ITT) Population for safety and tolerability is defined as all subjects who receive at least one dose of study drug or RT. The Per-Protocol (PP) Population for safety and tolerability is defined as all subjects who received at least 75% of the scheduled doses of study drugs and RT over the first 2 cycles, as well as, respective safety assessments (up to and including the pre-dose assessments scheduled for Cycle 3) without major protocol violations over the entire Cohort A concurrent ipilimumab and nivolumab assessment period (as defined in Section 3.1.9).

For both cohorts, the overall analysis of safety and tolerability will be based on the ITT Population.

Appropriate summaries of AEs, laboratory data, and vital sign data will be presented. AEs will be listed individually per subject according to the NCI CTCAE, Version 4.03, and the number of subjects experiencing each AE will be summarized using descriptive statistics.

CONFIDENTIAL

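### The Cohort A safety gate counts only Grade 3 or 4 related events, so a subject whose only severe related event is fatal (Grade 5) before Cycle 3 is left out of the count and replaced

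*Combined protocol and SAP*

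**What the plan says.** The gate appears four times, each time limited to Grade 3 or 4:

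- Synopsis: "subjects have Grade 3 or 4 drug- or radiation-related adverse events, the safety of Cohort A will be deemed acceptable" (when 7 or fewer are affected).
- Section 3.1, Cohort A: "subjects have Grade 3 or 4 drug- or radiation-related AEs, as per Section 3.1.6".
- Section 3.1.6: "A rating of Grade 3/4 drug- or radiation-related toxicity is considered to be acceptable in Cohort A if" no more than 7 of 9 (78%) are affected.
- Section 3.1.9: "subjects have Grade 3 or 4 drug- or radiation-related AEs, the safety of Cohort A will be deemed acceptable". This section also sets the assessment window: the first two cycles, through the Cycle 3 pre-dose safety assessments.

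Section 3.1.11 gives two ways to be evaluable for the Cohort A safety review. Criterion 1 is that "they receive at least 1 dose of ipilimumab, nivolumab, or RT and have a Grade 3 or 4 related AE". Criterion 2, for subjects without such an event, is membership of the safety Per-Protocol population. Section 4.1.2 defines that population as needing at least 75% of doses over two cycles and safety assessments "up to and including the pre-dose assessments scheduled for Cycle 3" (Day 43 ± 3 in the flowchart). For anyone meeting neither criterion: "Subjects in Cohort A who are not fully evaluable for safety review will be replaced".

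The same section treats subjects as evaluable for the secondary efficacy endpoints "if they discontinue from the study due to symptomatic progression, death, or toxicity at any point". It has no matching provision for the safety review.

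**The concern.** On the CTCAE scale that the protocol adopts, a fatal event is Grade 5. Read literally, the gate and criterion 1 leave Grade 5 out, and a subject who dies before the Cycle 3 pre-dose visit cannot have the assessments that criterion 2 needs. The worst possible related outcome therefore makes the subject non-evaluable, and replacement is mandatory.

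What is at stake is the go/no-go decision for Cohort B, the only place where the protocol compares a toxicity count with a fixed limit. The panel would know of the death, but the number it must compare with 7 of 9 would not contain it, and a new subject would fill the place.

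**Working it through.** **Step 1: follow one subject through the text.** Take a Cohort A subject who has received at least one dose, whose only severe related event is recorded as Grade 5, and who dies before Cycle 3 pre-dose.

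| Rule | Result |
|---|---|
| Gate count (Synopsis, 3.1, 3.1.6, 3.1.9) | Not counted: no Grade 3 or 4 related event |
| Criterion 1 (3.1.11) | Not met, same reason |
| Criterion 2 (3.1.11, 4.1.2) | Not met: no Cycle 3 pre-dose assessments |
| Replacement (3.1.11) | Mandatory |

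The gap has limits. A subject who also has a recorded, non-exempt Grade 3 or 4 related event in the window is already counted. A death after Cycle 3 pre-dose is outside the window under either wording.

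**Step 2: reproduce the plan's figure.** 7/9 = 77.8%, which rounds to the stated 78%. With X ~ Bin(9, 0.53), P(X ≤ 7) = 0.970, so the gate passes 97.0% of the time at the 53% rate cited in Section 3.1.6.

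**Step 3: boundary example.** Of the first nine subjects, 7 have Grade 3/4 related events, 1 has a Grade 5-only death and 1 has neither.

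- Grade 5 counted: 8/9 = 88.9% affected, above the limit, so the gate fails.
- As written: the dead subject is replaced. If the replacement has no Grade 3/4 related event, the count is 7 of 9 and Cohort B opens. If it has one, the gate fails.

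**Step 4: average effect.** Let p be the probability of a Grade 3/4 related event in the window, and q the probability of a Grade 5-only related event in the window, disjoint from p. The documents give no q, so 1%, 2% and 5% are assumed. For p, 53% is the cited rate for the drugs without radiotherapy; 70% is assumed, because no rate exists for the triple regimen. Other reasons for non-evaluability are ignored.

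- As written (Grade 5-only subjects replaced until nine are evaluable): X ~ Bin(9, p/(1−q)).
- Grade 5 counted: X ~ Bin(9, p+q).
- The gate passes if X ≤ 7.

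| p | q | Pass, as written | Pass, Grade 5 counted | Rise (points) |
|---|---|---|---|---|
| 0.53 | 1% | 0.9682 | 0.9662 | 0.20 |
| 0.53 | 2% | 0.9658 | 0.9615 | 0.43 |
| 0.53 | 5% | 0.9574 | 0.9442 | 1.33 |
| 0.70 | 1% | 0.7911 | 0.7856 | 0.55 |
| 0.70 | 2% | 0.7774 | 0.7660 | 1.14 |
| 0.70 | 5% | 0.7302 | 0.6997 | 3.05 |

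**Step 5: how often the boundary pattern arises.** The 7+1+1 pattern has probability 9!/(7!·1!·1!) × p⁷ × q × (1−p−q), where the multinomial coefficient is 72. At p = 0.53 this is 0.0039, 0.0076 and 0.0178 for q = 1%, 2% and 5%. Given the pattern, the rule as written opens Cohort B with probability 1 − p/(1−q) = 0.465, 0.459 and 0.442. With Grade 5 counted it never does.

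**The case against.** The best counter-argument is that the gap is narrow, already backstopped, and negligible in its effect on the decision.

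- **Other safeguards.** Section 3.1.14 provides for suspension or a possible stop after a single unexpected death that is at least probably related, a far stricter trigger than 8 of 9. The medical monitor and the panel may also act at their discretion, and SAEs are reported within 24 hours. This stands, but a death judged expected, or only possibly related (a category in Section 7.1.4), has no automatic trigger. None of these rules alters the gate count or the replacement.
- **ITT reporting.** The overall safety analysis is ITT (Section 4.1.2), so no final table loses the death. True, but those tables do not decide whether Cohort B opens.
- **The inputs may run high.** Section 3.1.6 gives 53% with no two-cycle window and no amylase/lipase exception, and q could be below 1%. This also stands. With the same formulas, an assumed p of 0.40 gives rises of 0.05, 0.10 and 0.35 points for q = 1%, 2% and 5%, and p of 0.30 gives 0.01, 0.02 and 0.08. At p = 0.53, q of 0.1% or 0.5% gives 0.02 or 0.10.
- **The boundary case is rare.** At p = 0.53, multiplying the two probabilities in Step 5 gives about 0.2% (0.0039 × 0.465) to 0.8% (0.0178 × 0.442).
- **A permissive gate by design.** Section 3.1.6 calls the study descriptive and says the limit was chosen to avoid closing early. That explains the choice of 7 of 9, not the omission of deaths from the count.
- **Recording convention.** The documents never use the term Grade 5, and a fatal event might be entered at Grade 4. If so, the gap closes by a data-entry habit that the protocol does not state.

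These points bear on size. None supplies the missing rule.

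**Conclusion.** The concern holds. As written, a Grade 5-only related death before Cycle 3 pre-dose is removed from the Cohort A gate and the subject is replaced, and nothing elsewhere in the protocol corrects this. The protocol uses at-or-above grade wording in other places (Sections 2.2 and 8.3), so the limit to Grades 3 and 4 cannot be read as shorthand with confidence.

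The average effect on the decision is small: 0.2 to 1.3 points at a 53% rate and 0.6 to 3.1 points at 70%, for assumed Grade 5-only rates of 1% to 5%, and less if the in-window rates are lower. The consequence is material only near the boundary. The textual finding rests on one assumption, that a fatal event is recorded as Grade 5 under CTCAE 4.03. The sizes rest on the assumed q and on applying 53% or 70% to the two-cycle window. The point should be fixed because it concerns how a related death is counted and costs almost nothing to put right.

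**What to change.** In the Synopsis and Sections 3.1, 3.1.6, 3.1.9 and 3.1.11, define the counted event, and criterion 1 for evaluability, as a related AE of *Grade 3 or higher (including Grade 5)*. Keep the exception for asymptomatic amylase and lipase abnormalities. Carry the same change into the opening condition of criterion 2, so that the two criteria stay complementary. Add one sentence to Section 3.1.11: a Cohort A subject with a related death in the assessment period is evaluable, counts as affected and is not replaced.

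The cost is one phrase in five places plus one sentence, with no added subjects, data or procedures. The gate becomes slightly harder to pass: by 0.2 to 1.3 points at a 53% rate for the assumed Grade 5-only rates of 1% to 5%.

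### The amylase/lipase exclusion applies to the Cohort A event count but not to the evaluability rules in Section 3.1.11, so an under-exposed early drop-out can be kept as a non-event

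*Combined protocol and SAP*

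**What the plan says.** **Event count.** Sections 3.1, 3.1.6 and 3.1.9 accept Cohort A, and open Cohort B, if no more than 7 of 9 subjects have a Grade 3 or 4 drug- or radiation-related adverse event. The note in Section 3.1.9 says that Grade 3 or 4 "amylase or lipase abnormalities that are not associated with clinical symptoms will not be included in the Cohort A safety assessment". Section 3.1 has the same note, the Synopsis refers to it, and Section 3.1.6 repeats that "asymptomatic amylase and lipase abnormalities are not included". The assessment period is the first two cycles, up to the Cycle 3 pre-dose assessments.

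**Evaluability.** Section 3.1.11 gives two ways for a Cohort A subject to be fully evaluable:
- Item 1: "they receive at least 1 dose of ipilimumab, nivolumab, or RT and have a Grade 3 or 4 related AE".
- Item 2: "In the absence of a Grade 3 or 4 related AE, they fulfill the criteria for the Per-protocol population for safety and tolerability". Section 4.1.2 defines that population by "at least 75% of the scheduled doses of study drugs and RT over the first 2 cycles", plus safety assessments through Cycle 3 pre-dose and no major violations.

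Neither item mentions the exclusion or refers to it. The section then states: "Subjects in Cohort A who are not fully evaluable for safety review will be replaced".

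**Timing.** Section 3.1.9 says: "A safety review will be conducted when 9 subjects have been accrued to Cohort A and completed the concurrent ipilimumab and nivolumab therapy".

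**The concern.** Accepting a subject as evaluable after one dose is sound when the qualifying event is itself counted, because the outcome is then already known. It is not sound when the qualifying event is one that the count ignores. In that case the laboratory value exempts the subject from the exposure and observation requirement of item 2 and also leaves the subject scored as free of toxicity. One of the nine places goes to someone who may have been treated and observed for only part of the assessment period.

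The effect runs one way, toward finding Cohort A acceptable, and this is the numerical rule that decides whether the hypofractionated cohort opens. The version history in Section 8.1 suggests an oversight. Amendment 3 added the exclusion to Sections 3.1 and 3.1.9. Amendment 4 clarified it elsewhere and also edited Section 3.1.11, but did not carry the exclusion across.

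**Working it through.** **The plan's own figure.** 7/9 = 0.778, the 78% in Section 3.1.6. The plan states no error rate or operating characteristic to reproduce.

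**Step 1: two drop-outs side by side.** Both subjects receive Cycle 1 and leave before Cycle 2 for a reason unrelated to pancreatic enzymes. Each has had 1 of 2 scheduled doses of each antibody (50%, below the 75% required) and no Cycle 3 pre-dose assessment.

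| | No Grade 3/4 related event | Only an asymptomatic Grade 3 lipase, recorded as a related event |
|---|---|---|
| Item 1 | not met | met |
| Item 2 | applies, not met | does not apply |
| Status | replaced | kept |
| Event count (Section 3.1.9) | not in the nine | in the nine, not an event |

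**Step 2: effect on the rule.** Let k be the number of the nine places held by such subjects who end without a countable event. Let p be the true event rate in the others, taken as independent. The result is unacceptable only with 8 or more events:
- k = 0: 9p⁸(1−p) + p⁹
- k = 1: p⁸
- k = 2: 0, since at most 7 events are possible

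At p = 0.53: 9(0.00623)(0.47) + 0.00330 = 0.0296 for k = 0, and 0.53⁸ = 0.0062 for k = 1. At p = 0.90: 9(0.43047)(0.10) + 0.38742 = 0.7748, and 0.9⁸ = 0.4305 (0.43047 before rounding).

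| True rate p | k = 0 | k = 1 | k = 2 |
|---|---|---|---|
| 53% (Section 3.1.6, antibodies without RT) | 3.0% | 0.6% | 0% |
| 80% (assumed) | 43.6% | 16.8% | 0% |
| 90% (assumed) | 77.5% | 43.0% | 0% |
| 95% (assumed) | 92.9% | 66.3% | 0% |

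**Step 3: averaging over how often it happens.** The documents give no frequency, so assume that each subject has probability q of being such a case. Terms with k of 2 or more contribute nothing, so the averaged chance is (1−q)⁹P₀ + 9q(1−q)⁸P₁, where P₀ and P₁ are the k = 0 and k = 1 values. At q = 1% and p = 90%: 0.9135 × 0.7748 + 0.0830 × 0.4305 = 0.744.

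| Assumed q | Two or more among 9 | Averaged, p = 53% | Averaged, p = 90% |
|---|---|---|---|
| 0 | 0% | 3.0% | 77.5% |
| 1% | 0.3% | 2.8% | 74.4% |
| 2% | 1.3% | 2.6% | 71.2% |
| 5% | 7.1% | 2.1% | 61.7% |
| 10% | 22.5% | 1.4% | 46.7% |

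**Step 4: if the drop-out may still have a countable event.** Let r be the assumed chance of a later countable event inside the window, with the others at 90%.
- One such subject: r × 0.8131 + (1−r) × 0.4305, where 0.8131 is the chance of at least 7 events in 8. This gives 46.9% at r = 10% and 62.2% at r = 50%.
- Two such subjects: r² × 0.8503 + 2r(1−r) × 0.4783, where 0.8503 is the chance of at least 6 events in 7 and 0.4783 = 0.9⁷. This gives 9.5% at r = 10% and 45.2% at r = 50%.

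**The case against.** **These subjects are not certain non-events.** A reader might infer that each one is a guaranteed zero. Sections 3.1.10, 3.1.16 and 7.1.5 keep subjects withdrawn from treatment under adverse event collection for 100 days, and nothing closes the assessment window at withdrawal. This stands: the k = 1 and k = 2 columns hold only where no countable event follows, and Step 4 shows the softer case. Follow-up does not cure the under-exposure, and it does not reach subjects who withdraw consent for all follow-up or are lost.

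**The exclusion may already govern evaluability.** Section 3.1.11 defines evaluability for the safety review, and the note in Section 3.1.9 removes these abnormalities from the Cohort A safety assessment. Timing the review to nine subjects who completed concurrent therapy also sits badly with one-dose evaluability. That reading is possible, but Section 3.1.11 does not state it, and two people applying the text could settle on different sets of nine.

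**The case needs several things together.** The finding must be recorded as an adverse event (Section 4.1.1 requires the investigator to judge it clinically significant; Section 7.1.1 is broader) and judged related. No other related Grade 3 or 4 event may occur. The early exit needs another cause, because Section 8.3 requires neither delay for asymptomatic Grade 3 values nor discontinuation for isolated asymptomatic Grade 4 values. Section 3.1.8 also recommends giving all four doses despite apparent progression if performance status is stable. This limits the likelihood but does not remove the inconsistency.

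**The 0% is not specific to this defect.** A reader might infer that Section 3.1.11 disables the rule. Any two non-events satisfy a limit of 7 of 9, a limit that Section 3.1.6 says was chosen to avoid closing too early. What is specific here is that the two may be subjects who would otherwise have been replaced.

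**Other controls exist.** Section 3.1.2 puts enrollment under ongoing panel review, Section 3.1.14 lists grounds for suspension, and Section 4.1.2 bases the overall safety analysis on all treated subjects. This stands and limits the harm.

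**Conclusion.** The inconsistency is real and should be corrected. As written, the Cohort A count and Section 3.1.11 use different event definitions, and the gap favors acceptance. Where one affected subject ends without a countable event, the chance of an unacceptable result falls by 2.4 percentage points at the protocol's 53% rate (3.0% to 0.6%) and by about 34 points at an assumed 90% rate (77.5% to 43.0%). The expected effect is smaller: at an assumed frequency of 1% to 5% per subject, the loss at the 90% rate is about 3 to 16 points.

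These figures assume independent subjects with a common event rate. The event rates above 53% and every frequency are assumptions. The missing exclusion is certain from the text; how often it would matter is not. The documents do not support concluding that the rule was made unable to fail, or that Cohort B would open without other safety oversight.

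**What to change.** Use one event definition in Sections 3.1.9 and 3.1.11. In item 1 of Section 3.1.11, qualify the related event with *that counts toward the Cohort A safety assessment (i.e., excluding asymptomatic amylase or lipase abnormalities, Section 3.1)*. Begin item 2 with *In the absence of such an AE*. A subject with only an excluded laboratory finding must then meet the Per-Protocol criteria or be replaced. In the same edit, reconcile one-dose evaluability with the statement in Section 3.1.9 that the nine subjects have completed concurrent therapy.

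The limit of 7 of 9 and all clinical management stay as they are. The cost is a short amendment and an occasional extra subject under the existing replacement rule.
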